## PROTOCOL AMENDMENT SUMMARY OF CHANGES TABLE

Document History		
Document	Date	Type of amendment
Amendment 6	21 Mar 2024	Nonsubstantial
Amendment 5	30 Jun 2023	Substantial
Amendment 4	24 Feb 2022	Substantial
Amendment 3	04 Oct 2021	Substantial
Amendment 2.2 UK	04 Jun 2021	Nonsubstantial
Amendment 2.1 France	04 Jun 2021	Nonsubstantial
Amendment 2	21 May 2021	Nonsubstantial
Amendment 1.7 Germany	10 Aug 2021	Substantial a
Amendment 1.6 Germany	17 May 2021	Nonsubstantial
Amendment 1.5 Germany	01 Apr 2021	Nonsubstantial
Amendment 1.4 UK	25 Feb 2021	Not applicable
Amendment 1.3 Germany	22 Feb 2021	Not applicable
Amendment 1.2 France	17 Feb 2021	Not applicable
Amendment 1.1 Canada	15 Feb 2021	Not applicable
Amendment 1	29 Oct 2020	Not applicable
Original Protocol	13 Oct 2020	Not applicable

a Amendment 1.7 Germany was initially submitted as a nonsubstantial amendment.

### Amendment 6 (21 Mar 2024)

PD0053 Protocol Amendment 6 was completed to provide clarification around blinding, the timing of the Month 12 data analysis, and to remove analyses that are no longer needed. In addition, the list of secondary and exploratory efficacy endpoints was updated. The following changes were implemented:

Section # and Name	Description of Change	Brief Rationale
Global	Throughout the protocol, references to PD0055 were updated to clarify that this is a dose-blinded (not an open-label) extension study.	Correction.

Section # and Name	Description of Change	Brief Rationale

Section 1.1 Synopsis Objectives and Endpoints and Section 3 OBJECTIVES AND ENDPOINTS
	
A new Secondary Efficacy Endpoint for the primary efficacy objective was added and replaces the former exploratory endpoint 'MDS-UPDRS selected items' (as described below):
 
 
• MDS-UPDRS Part III ePD subscore on selected items (timeframe: Baseline to 18 months)
 
	
To add a new secondary efficacy endpoint based on the MDS-UPDRS Part III subscale.

	
A new Secondary Efficacy Endpoint was added for the primary efficacy objective:
 
 
• Emerging symptoms as measured by MDS-UPDRS Part II (timeframe: Baseline to 18 months)
 
	
To add a new secondary efficacy endpoint consisting of an additional analysis of the MDS-UPDRS Part II data already collected in the study.

	
The following Secondary Efficacy Endpoint for the primary efficacy objective was revised (bolded text added):
 
 
• Time to worsening of the disease as measured by MDS-UPDRS Part III (timeframe: Baseline to 18 months)
 
	
To further specify the endpoint.

	
The following Exploratory Efficacy Endpoint for the primary efficacy objective was revised (see strikethrough text):
 
 
• Time to worsening in MDS-UPDRS Part I and Part II subscales
 
	
To further specify the endpoint (Part II subscale is removed as it is now part of new secondary emerging symptoms endpoint).

	
The following Exploratory Efficacy Endpoint for the primary efficacy objective was removed and is now covered by the new secondary endpoint 'MDS-UPDRS Part III ePD subscore (selection of items)':
 
 
• <del>MDS UPDRS selected items</del>
 
	
To modify an exploratory efficacy endpoint: this endpoint is now part of the secondary endpoints.

	
A new Exploratory Efficacy Endpoint was added for the primary efficacy objective:
 
 
• Composite endpoint (based on MDS-UPDRS and/or Early PD PROs)
 
	
To add an exploratory efficacy endpoint composed of endpoints already included in the study.

Section # and Name	Description of Change	Brief Rationale
Section 1.1 Synopsis Objectives and Endpoints	The Exploratory Efficacy Endpoint ‘CSF ASYN oligomers/seeding capacity’ was added for the secondary efficacy objective.	To align with Section 3 (implementing a change from Amendment 4 that was missed in Amendment 5).
Section 1.3 Schedule of Activities	Footnote ‘b’ was removed from V9. Footnote ‘b’ was added to V16.	Correction. To align with the visits that can be done from the participant’s home.
Section 5.2 Exclusion criteria	In exclusion criterion #31b (1) (previously #31a [1]), bupropion was added back.	Correction. Bupropion had inadvertently been removed in Amendment 4.
Section 6.3 Measures to minimize bias: randomization and blinding	In the fifth paragraph, the following bullet was added to further clarify who may have access to the randomization code: 

• Unblinded pharmacometrics staff and statistical programmers, independent from the study team, who have access to the 12-month data for the preparation of the exposure-response analysis

	To add access to the randomization code to independent experts for exposure-response model development, which has no impact on the ongoing study monitoring and conduct.
Section 6.5.2 Prohibited concomitant treatments (medications and therapies)	Bupropion was added to the list of medications that are not allowed during the 50 days before DaT-SPECT imaging.	To complete the list of drugs that may affect the DaT-SPECT scan.
Section 8.1.1.1 MDS-UPDRS	The introductory sentence for the MDS-UPDRS was revised to clarify that the 4 parts are referred to as “subscales.”	To clarify terminology.
Section 9.3 Planned efficacy/outcome analyses	Table 9-1 was updated to reflect the updates to secondary and exploratory efficacy endpoints.	To align with updates to the list of exploratory efficacy endpoints in objectives and endpoints table.
	Text below Table 9-1 was updated to clarify that the efficacy data analysis will take place once all participants have completed their 18-month Visit.	To clarify the timepoint of the efficacy analysis.

Section # and Name	Description of Change	Brief Rationale
Section 9.3 Planned efficacy/outcome analyses	Text around sensitivity analyses was removed at the end of the section.	To remove sensitivity analyses that are no longer relevant due to the large proportion of participants having initiated ST during the study, and/or due to the data being unblinded at end of study only and not at Month 12.
Section 9.3.1.1.1 Primary Efficacy Estimand: MDS-UPDRS Parts I-III sum score at 12 months (“De Jure” Estimand) and Section 9.3.1.2.3 Secondary Efficacy Estimand: MDS-UPDRS Part I/Part II/Part III subscales at 18 months (“De Jure” Estimand)	Under ICEs and handling strategies , ‘while-on-treatment’ was updated to ‘hypothetical’.	Updated to use ‘hypothetical’ in place of ‘while-on-treatment’ throughout (no change to actual handling of data, post-ICE data will still be set to missing).
Section 9.3.1.1.1 Supplementary Efficacy Estimand to MDS-UPDRS Parts I-III sum score at 12 months (“De Facto” Estimand)	Under Estimator , text was updated to refer to Section 9.3.1.2.1.1 (LMM estimator based on Baseline to Month 18 data).	Separate 12-month analyses will not be performed. Estimates at Month 12 will be generated from the analyses over 18 months.

Section # and Name	Description of Change	Brief Rationale

Section 9.3.1.1.1 Primary Efficacy Estimand: MDS-UPDRS Parts I-III sum score at 12 months (“De Jure” Estimand) and Section 9.3.1.1.2 Key Secondary Efficacy Estimand: MDS-UPDRS Part III subscale at 12 months (“De Jure” Estimand) and Section 9.3.1.1.4 Secondary Efficacy Estimands: MDS-UPDRS Part I/II subscales at 12 months (“De Jure” Estimands) and Section 9.3.1.2.1 Key Secondary Efficacy Estimand: MDS-UPDRS Parts I-III sum score at 18 months (“De Jure” Estimand) and Section 9.3.1.2.5 (previously 9.3.1.2.4) Secondary Efficacy Estimand: MoCA over 18 months
	
Subheading and text for Sensitivity analyses was removed.
	
Sensitivity analyses for these estimands are no longer relevant.


Section 9.3.1.1.3 Key Secondary Efficacy Estimand: Worsening on MDS-UPDRS Part III subscale at 12 months (“De Jure” Estimand)
	
Section was removed.
	
To remove a time-to-event analysis which has become redundant as unblinding will only occur at end of study.

Section 9.3.1.1.3 Key Secondary Efficacy Estimand: MDS-UPDRS Part III subscale and Part III early-stage PD subscore at 12 months
	
New section was added.
	
To align with updates to the list of exploratory efficacy endpoints in objectives and endpoints table.

Section 9.3.1.1.4 Secondary Efficacy Estimands: MDS-UPDRS Part I/II subscales at 12 months (“De Jure” Estimands)
	
Text under ICEs and handling strategies and Population-level summary was updated.
	
Correction to handle MDS-UPDRS Part I and Part II in the same way for the secondary estimand, and handle both regardless of ST in the supplementary estimand.

Section # and Name	Description of Change	Brief Rationale
Section 9.3.1.1.4 Secondary Efficacy Estimands: MDS-UPDRS Part I/II subscales at 12 months (“De Jure” Estimands)	Under Estimator , text was replaced to be a reference to Section 9.3.1.2.3 (LMEM estimator based on Baseline to Month 18 data).	Separate 12-month analyses will not be performed. Estimates at Month 12 will be generated from the analyses over 18 months.
Section 9.3.1.1.4.1 Supplementary Efficacy Estimand to MDS-UPDRS Part I/II subscales at 12 months (“De Facto” Estimand)	Under Estimator, estimates, and sensitivity analyses , text was replaced to be a reference to Section 9.3.1.2.1.1 (LMEM estimator based on Baseline to Month 18 data).	Separate 12-month analyses will not be performed. Estimates at Month 12 will be generated from the analyses over 18 months.
Section 9.3.1.1.5 Exploratory Efficacy Endpoints at 12 months and Section 9.3.1.2.6 (previously 9.3.1.2.5) Exploratory Efficacy Endpoints at 18 months	
The first Exploratory Efficacy Endpoint in the list was updated (see strikethrough text):
 
 
Time to worsening in MDS-UPDRS Part I <del>and Part II</del> subscales
 
 
The second Exploratory Efficacy Endpoint in the list was removed:
 
 
<del>MDS-UPDRS selected items</del>
 
 
A new Exploratory Efficacy Endpoint was added below the Mobility PRO:
 
 
Composite endpoint (based on MDS-UPDRS and/or Early PD PROs)
 
	To align with updates in objectives and endpoints table.
Section 9.3.1.2.3 Secondary Efficacy Estimand: MDS-UPDRS Part I/Part II/Part III subscales at 18 months (“De Jure” Estimand)	Under Sensitivity analyses , text was updated.	To remove sensitivity analyses that are no longer relevant.
Section 9.3.1.2.3.1 Key Secondary Efficacy Estimand: MDS-UPDRS Part III subscale and Part III ePD subscore at 18 months	New section was added.	To align with updates to the list of exploratory efficacy endpoints in objectives and endpoints table.
Section 9.3.1.2.3.2 (previously 9.3.1.2.3.1) Supplementary Efficacy Estimand: MDS-UPDRS Part II/Part III subscales at 18 months (“De Facto” Estimand)	Under Estimator, estimates, and sensitivity analyses , a reference to the SAP for further exploratory analyses was removed.	To remove sensitivity analyses that are no longer relevant.

Section # and Name	Description of Change	Brief Rationale
Section 9.3.1.2.4 Secondary Efficacy Estimand: MDS-UPDRS Part II emerging symptoms over 18 months	New section was added.	To align with updates to the list of exploratory efficacy endpoints in objectives and endpoints table.
Section 9.3.2.1 Secondary Efficacy Estimand: DaT-SPECT mean Striatum SBR at Month 12 and Month 18	Throughout, references to “18 months” have been replaced by “Month 12 and Month 18” for clarity.  The text under Sensitivity analyses was updated.	To clarify that separate 12-month analyses will not be performed. Estimates at Month 12 will be generated from the analyses over 18 months.
Section 9.3.2.1.1 Supplementary Efficacy Estimand: DaT-SPECT mean Striatum SBR at 18 months	Section was removed.	To remove a supplementary analysis that is no longer relevant.
Section 9.3.2.2 Other Secondary Efficacy Estimand: DaT-SPECT mean Striatum SBR at 12 months	Section was removed.	Section no longer applies as no separate 12-month analyses will be done. Estimates at Month 12 will be generated from the main analyses over 18 months.
Section 9.3.2.2 (previously 9.3.2.3) Exploratory Efficacy Endpoints at Month 12 and Month 18	In the section title, “at 12 and 18 months” was changed to “Month 12 and Month 18.”	Minor editorial change.
Section 9.3.3.1 Secondary Efficacy Estimand: Time to ST initiation over 18 months	The section heading was corrected: “Time to ST <del>intake at initiation over 18 months”</del> The subheading Supplementary analyses and reference to the SAP was removed.	To remove supplementary analyses that are no longer relevant.
Section 9.3.3.2 Secondary Efficacy Estimand: Intake of ST at 18 months and Section 9.3.3.3 Other Secondary Efficacy Estimand: Intake of ST at 12 months	The following sentence was removed under Sensitivity analyses : <del>The main model will be adjusted for Baseline predictors of early initiation of ST.</del>	To remove sensitivity analyses that are no longer relevant.
Section 9.3.4 Subgroup analyses	Text was updated to clarify that analyses by subgroup will be performed as part of exploratory analyses.	To remove analyses that are no longer planned as part of the main analysis.

Section # and Name	Description of Change	Brief Rationale
Section 9.5 Handling of ICEs, protocol deviations, and resulting missing data	
The second bullet for the ‘while-on-treatment’ strategy was removed.
 
The third bullet for the ‘hypothetical’ strategy was revised.
 
The overview of handling strategies for MDS-UPDRS ICEs and study termination was updated (Table 9-2 and associated text).
	To remove the ‘while-on-treatment’ strategy and align with updates to efficacy endpoints throughout the protocol.
Section 9.5.1 ICEs potentially affecting the interpretation of measurements	
Under MDS-UPDRS, the description of how the post-ICE data will be censored was updated.
 
Under DaT-SPECT, the description of the supplementary analysis was removed.
 
Under Treatment discontinuation/nonadherence, ‘while-on-treatment’ strategy was replaced with ‘hypothetical’ strategy.
	To remove the DaT-SPECT supplementary analysis which was no longer relevant and to align with other changes made throughout the protocol, eg, to reflect change in wording of handling strategy from ‘while on treatment’ to ‘hypothetical’.
Section 9.5.3 Other protocol deviations	
In the fourth paragraph, ‘while-on-treatment’ strategy was replaced with ‘hypothetical’ strategy.
 
The eighth paragraph on the ‘while-on-treatment’ strategy was removed.
	To replace the ‘while-on-treatment’ strategy with ‘hypothetical’ strategy throughout and align with other changes made throughout the protocol.
Section 9.6 Planned analysis at 12 months and data monitoring	
The first paragraph was revised to clarify that the analyses of Month 12 data will be carried out at study end.
 
A paragraph was added to describe that a limited team of independent pharmacometrists and statistical programmers with access to the 12-month data will be unblinded to prepare for the exposure-response analysis.
	To clarify that no primary analysis at Month 12 will be done, and to describe the unblinding of an independent expert group to develop the exposure-response model which has no impact on the study monitoring or conduct.
Section 10.6 Appendix 6: Liver safety suggested actions and follow-up assessments	
In Table 10-1 (Phase 2 Liver Chemistry Stopping Criteria and Follow-up Assessments), GGT was added as an optional follow-up assessment.
	To better characterize the important potential UCB0599 risk of transaminases elevation in case of potential drug-induced liver injury.

Section # and Name	Description of Change	Brief Rationale
Section 11 REFERENCES	The following reference was added: Tosin et al, 2022. The following references were removed: Mehrotra et al, 2017; Parashos et al, 2009; Simuni et al, 2016.	To add a new reference and to remove references that are no longer cited.
Throughout	Minor editorial and document formatting revisions.	Minor, therefore have not been summarized.

PUBLIC COPY  
This document cannot be used to support any marketing authorization application  
and any extensions or variations thereof.

## 1 PROTOCOL SUMMARY

### 1.1 Synopsis

#### Protocol title:

A double-blind, placebo-controlled, randomized, 18-month Phase 2a study to evaluate the efficacy, safety, tolerability, and pharmacokinetics of oral UCB0599 in study participants with early Parkinson's disease

#### Short Title:

A double-blind, placebo-controlled, randomized, Phase 2a study with oral UCB0599 in study participants with early Parkinson's disease

#### Rationale:

UCB0599 is an orally available inhibitor of alpha-synuclein (ASYN) misfolding and downstream aggregation. Aggregated forms of ASYN are the hallmark fibrillar protein deposits in Parkinson's disease (PD) and other synucleinopathies, and evidence suggests that it is the misfolded forms of ASYN that propagate through the central nervous system (CNS) during disease progression. These accumulations of ASYN-containing neuronal inclusions form Lewy bodies and Lewy neurites.

Nonclinical and in vivo pharmacology studies have provided scientific evidence suggesting that UCB0599 may slow disease progression in PD, which remains the main unmet medical need in this condition. A first-in-human (FIH) study using UCB0599, UP0030, was conducted in healthy elderly participants. UP0030 provided the safety, tolerability, and pharmacokinetic (PK) information for single dose exposures up to 450mg and multiple dose exposures of 180mg/day for up to 21 days in healthy elderly participants (defined as  $\geq 55$  to  $\leq 75$  years of age). The first study in the target population, UP0077, provided safety, tolerability, and PK information for multiple dose exposures of 180mg/day and 360mg/day for 28 days in study participants with PD. UP0077 also provided information for the design of the current proof-of-concept (POC) study in study participants with early-stage PD. PD0053 is designed to provide proof of concept for the efficacy of the synuclein misfolding inhibitor UCB0599 in reducing disease progression in study participants with early-stage PD and to instruct later stage development.

#### Objectives and Endpoints

Objectives	Endpoints
Primary Efficacy Objective	
To demonstrate the superiority of UCB0599 over placebo with regard to clinical symptoms of disease progression over 12 and 18 months in participants diagnosed with early-stage PD	Primary Efficacy Endpoint 

MDS-UPDRS Parts I-III sum score (timeframe: Baseline to 18 months)

 Secondary Efficacy Endpoints 

MDS-UPDRS Part III subscale (timeframe: Baseline to 18 months)

MDS-UPDRS Part III ePD subscore on selected items (timeframe: Baseline to 18 months)

Objectives	Endpoints
	

• MDS-UPDRS Part II subscale (timeframe: Baseline to 18 months)

• MDS-UPDRS Part I subscale (timeframe: Baseline to 18 months)

• Emerging symptoms as measured by MDS-UPDRS Part II (timeframe: Baseline to 18 months)

• Time to worsening of the disease as measured by MDS-UPDRS Part III (timeframe: Baseline to 18 months)

• MoCA (timeframe: Baseline to 18 months)

 
Exploratory Efficacy Endpoints
 

• Time to worsening in MDS-UPDRS Part I subscale

• Modified Hoehn and Yahr staging

• CGII

• CGIS

• Fatigue-PRO

• Early PD Function Slowness PRO

• Early PD Mobility PRO

• Composite endpoint (based on MDS-UPDRS and/or Early PD PROs)

• PGIS, overall and fatigue-specific

• PGIC, overall and fatigue-specific

• SE-ADL

• HADS

• MDS-NMS

• Starkstein Apathy Scale

• EQ-5D-5L

• Wearable sensor

Objectives	Endpoints
Secondary Efficacy Objectives	
To demonstrate the superiority of UCB0599 over placebo with regard to neurodegeneration of dopaminergic neurons over 12 and 18 months in participants diagnosed with early-stage PD	
Secondary Efficacy Endpoints
 
 
Change from Baseline (Screening) in DaT-SPECT mean Striatum SBR (timeframe: Screening to 18 months)
 
 
Exploratory Efficacy Endpoints
 
 
DaT-SPECT mean SBR in striatal subregions
 
CSF total ASYN
 
CSF ASYN oligomers/seeding capacity
 

To assess the effect of UCB0599 vs placebo with regard to intake of ST over 18 months in participants diagnosed with early-stage PD	
Secondary Efficacy Endpoints
 
 
Time to start of ST (timeframe: Baseline to 18 months)
 
ST intake (timeframe: Baseline to 18 months)
 
 
Exploratory Efficacy Endpoints
 
 
Levodopa cumulative daily dose
 

Primary Safety Objective	
To assess the safety and tolerability of UCB0599 in participants diagnosed with early-stage PD	
Secondary Safety Endpoints
 
 
Incidence of TEAEs
 
Incidence of SAEs
 
Incidence of TEAEs leading to participant withdrawal
 
 
Other Safety Endpoints
 
 
Change from Baseline in clinical laboratory values (chemistry, hematology, and urinalysis)
 
Change from Baseline in vital signs
 
Change from Baseline in physical examination
 
Change from Baseline in neurological examination findings
 
C-SSRS findings
 
ECG findings
 

Exploratory PK Objective	
To assess the PK of UCB0599 and its N-oxide metabolite in participants diagnosed with early-stage PD	
Exploratory PK Endpoint
 
 
UCB0599 and N-oxide metabolite plasma and CSF concentrations
 

ASYN=alpha-synuclein; CGII=Clinical Global Impression of Improvement; CGIS=Clinical Global Impression of Severity; CSF=cerebrospinal fluid; C-SSRS=Columbia-Suicide Severity Rating Scale; DaT-SPECT=Dopamine Transporter Imaging with Single Photon Emission Computerized Tomography; ECG=electrocardiogram; ePD=early-stage PD; EQ-5D-5L=EuroQol-5-dimension-5-level; HADS=Hospital Anxiety and Depression Scale; MDS-NMS=Movement Disorder Society-Non-motor Scale; MDS-UPDRS=Movement Disorder Society-Unified Parkinson's Disease Rating Scale; MoCA=Montreal Cognitive Assessment; PD=Parkinson's disease; PGIC=Patient Global Impression of Change; PGIS=Patient Global Impression of Severity; PK=pharmacokinetic; PRO=Patient-Reported Outcome; SAE=serious adverse event; SBR=specific binding ratio; SE-ADL=Schwab and England Activities of Daily Living; ST=symptomatic treatment; TEAE=treatment-emergent adverse event

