### **8.2.6 Suicidal risk monitoring**

UCB0599 is a CNS-active study medication. There has been concern that some CNS-active study medications may be associated with an increased risk of suicidal ideation or behavior when given to some participants with PD.

Suicidality will be assessed by trained site study personnel using the C-SSRS (Posner et al, 2011). During remote visits, the assessment will be performed remotely via telemedicine. This scale will be used for Screening as well as to assess suicidal ideation and behavior that may occur during the study. All study participants will complete the “Baseline/Screening” version of the C-SSRS at Visit 1 (assessing the past 6 months), followed by the “Since Last Visit” version at the visits indicated on the Schedule of Activities (Section 1.3).

Participants being treated with UCB0599 should be monitored appropriately and observed closely for suicidal ideation and behavior or any other unusual changes in behavior. Families and caregivers of participants being treated with UCB0599 should be instructed to monitor participants for the emergence of unusual changes in behavior, as well as the emergence of suicidal ideation and behavior, and to report such symptoms immediately to the study Investigator. Consideration should be given to discontinuing UCB0599 in participants who experience signs of suicidal ideation or behavior. Study stopping behavior for study participants with suicidal ideation or behavior is described in Section 7.2.

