## **9.4 Planned safety and PK analyses**

### **9.4.1 Safety analyses**

Safety will be assessed by analyzing incidence of any TEAE, study participant withdrawals, and changes in different parameters such as vital signs, safety laboratory data, 12-lead ECG assessment, physical examination findings, neurological examination findings, and suicidality using the C-SSRS.

Further details on the planned safety analyses will be given in the SAP.

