5.4.3.4 Physical and neurological examination

Study participants with abnormalities in the physical and neurological examination will have this information listed including details of the abnormality.

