5.4.3.5 Suicidal risk monitoring

The Columbia-Suicide Severity Rating Scale (C-SSRS; Posner et al, 2011) evaluations include suicidal ideation, intensity of ideation, suicidal behavior, and actual attempts and will be performed at all study visits (except for screening visit 2). Module of the questionnaire, time point, question and the associated response will be listed for all visits where this questionnaire is collected by treatment group. Only data where suicidal ideation/behaviour has been reported needs to be included in the listing.

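### Physical examination, neurological examination and C-SSRS are declared safety endpoints, but the SAP plans listings only: the examination changes from Baseline are never produced and C-SSRS has no by-arm rate

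*Protocol*

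**What the plan says.** The objectives tables in Protocol 1.1 and Section 3, repeated in SAP Table 1-1, name three other safety endpoints that matter here: "Change from Baseline in physical examination", "Change from Baseline in neurological examination findings" and "C-SSRS findings".

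Protocol 9.4.1 describes the safety assessment as an analysis of "changes in different parameters such as vital signs, safety laboratory data, 12-lead ECG assessment, physical examination findings, neurological examination findings, and suicidality using the C-SSRS", and leaves the detail to the SAP.

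The opening sentence of SAP 5.4 commits to both summaries and listings of safety data per treatment group on the Safety Set. The two relevant subsections then give the following rules:

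- SAP 5.4.3.4: "Study participants with abnormalities in the physical and neurological examination will have this information listed including details of the abnormality". Nothing further is specified.
- SAP 5.4.3.5: a listing by treatment group with questionnaire module, time point, question and response, limited as follows: "Only data where suicidal ideation/behaviour has been reported needs to be included in the listing".

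Neither subsection plans a count, a percentage, a shift table or a change from Baseline. SAP Appendix 2, which records departures from the protocol-planned analyses, does not mention this one.

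**The concern.** Two of the three endpoints are defined as a change from Baseline, and a listing of abnormalities does not deliver a change. The third has no denominator and no rate in its own section, so a reader of the study report would have to count listing rows and divide by the arm size to compare arms.

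Protocol 8.2.6 describes UCB0599 as CNS-active and gives the reason for collecting the C-SSRS: "There has been concern that some CNS-active study medications may be associated with an increased risk of suicidal ideation or behavior". If that is why it is collected at nearly every visit, the report should say how many participants in each arm had post-dose ideation or behavior, and in how many this was new.

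The entry criteria make the new-case question a real one. Exclusion criterion 12 removes people with a lifetime attempt, or with a positive answer to Question 4 or 5 over the past 6 months. Lesser ideation may be present at entry. For the examinations, inclusion criterion 3 requires bradykinesia plus rigidity or resting tremor, and the neurological examination covers motor status and muscle tone. Some listed abnormalities may therefore be the disease itself, present before dosing.

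**Working it through.** No arithmetic applies. The check traces each declared safety endpoint to its planned output.

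| Measure | Declared as | Output in its SAP section | By-arm summary? |
|---|---|---|---|
| Laboratory | Change from Baseline | 5.4.3.1: observed and change by arm for chemistry and hematology; shift tables for selected variables | Yes |
| Vital signs | Change from Baseline | 5.4.3.2: observed and change by arm; number (%) markedly abnormal | Yes |
| ECG | Findings | 5.4.3.3: observed and change by arm; QTcF categories | Yes |
| Physical examination | Change from Baseline | 5.4.3.4: listing of abnormalities | No |
| Neurological examination | Change from Baseline | 5.4.3.4: listing of abnormalities | No |
| C-SSRS | Findings | 5.4.3.5: listing of positive reports | No |

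1. The other domains show that the SAP knows how to produce by-arm change summaries. ECG is a useful comparator for C-SSRS: it too is declared only as findings, yet it receives by-arm summaries and categories.

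2. Could a general rule fill the gap? SAP Section 1 says the protocol's analysis applies unless the SAP specifies otherwise. Here the SAP does specify something, and Protocol 9.4.1 contains no method to fall back on. The opening sentence of SAP 5.4 promises summaries but does not define them, so it shows an inconsistency within the SAP and supplies no analysis.

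3. Do other outputs cover the same data?
   - *Adverse events.* Protocol 8.2.1 and 8.2.2 turn clinically relevant or worsening physical findings, and clinically significant neurological findings, into AEs. Protocol 7.1 and Appendix 3 do the same in general terms for new clinically relevant findings and for safety assessments that worsen from Baseline; C-SSRS responses can enter this way. SAP 5.4.2 tabulates TEAEs by treatment group. This route depends on the investigator's judgment of relevance, and Appendix 3 excludes expected signs of the disease unless they are more severe than expected. It counts events and gives no change from Baseline.
   - *Modified Hoehn and Yahr.* It is collected with the neurological examination, and SAP 5.3.3.1 gives it by-arm frequencies and shift tables. It is one staging scale, reported as exploratory efficacy on the FAS, which excludes participants who fail key eligibility criteria (SAP Section 4 and Appendix 6). The examination also covers consciousness, cranial nerves, reflexes, coordination and sensation (Protocol 8.2.2).
   - *Physical examination.* Apart from the AE route, nothing else covers it.

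4. Is the reduction documented? SAP Appendix 2 lists changes to the FAS, the de-mediated estimands and the emerging-symptoms strategy. It lists nothing on these endpoints.

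**The case against.** The other side has good points, and several of them limit the claim.

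- C-SSRS is declared as findings, and a listing of findings by arm does not contradict that label. This stands as far as the objectives table goes. The commitment to analyze changes in suicidality comes from Protocol 9.4.1.
- The listing carries module and time point, so pre-dose and post-dose reports can be told apart row by row. This stands: the information is there, and what is missing is the tabulation.
- A reader might infer that no arm-level comparison of these data exists at all. The documents do not support that, because clinically relevant findings have a route to the by-arm TEAE tables and modified Hoehn and Yahr has shift tables.
- A reader might infer that a positives-only listing would show a spurious excess on active treatment because two arms are active. The listing is by treatment group, so that impression arises only if the reader pools the doses. Arm sizes in the Safety Set are reported under SAP 5.2.
- A reader might infer from inclusion criterion 3 that nearly every neurological examination will be recorded as abnormal. The documents do not say how an abnormality is coded or whether expected signs of the disease count.
- Suicidality is not among the risks that Protocol 2.3 names for UCB0599; Protocol 8.2.6 speaks of CNS-active medications in general. The DMC also reviews unblinded safety data during the study (SAP 5.9).
- SAP Table 6-1 has a row for other safety analyses and defers to the TFL shells, which are not part of these documents. The shells may hold more, but the SAP's own rule for these endpoints is a listing.

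None of this supplies a summary of the declared endpoints.

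**Conclusion.** The mismatch is real and confined to three other safety endpoints. Following the SAP as written, the change from Baseline in physical examination and in neurological examination findings is never produced, and C-SSRS has no by-arm count or rate. The SAP also contradicts its own general rule in 5.4, and the reduction is not logged.

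This is a reporting gap that is cheap to close. It has no bearing on sample size, alpha or the primary analysis, and it is not evidence of a safety signal. The conclusion rests on reading SAP 5.4.3.4 and 5.4.3.5 as complete specifications, with no additional tables held only in the shells.

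**What to change.** **SAP 5.4.3.5.** Add a by-arm table on the Safety Set with at least one post-dose C-SSRS, giving number (%) with:

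- any post-dose suicidal ideation, by highest level;
- any post-dose suicidal behavior;
- emergent cases, defined as worse than the worst pre-dose assessment.

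The pre-dose assessments are Screening V1 and Baseline V3. Both are needed: the Schedule of Activities has C-SSRS at each, and SAP 5.1.2.1.5 takes Baseline as the latest pre-dose value. A comparison with V1 alone would count ideation first reported at V3, before dosing, as emergent. A comparison with V3 alone would ignore the 6-month look-back at V1.

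**SAP 5.4.3.4.** For each of the two examinations, add a by-arm shift table from Baseline to worst post-baseline result, or number (%) with a new abnormality by body system. Complete, brief and telemedicine examinations do not cover the same systems (Protocol 8.2.1 and 8.2.2), so the text should say that each system is compared with its own last pre-dose assessment.

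Keep both listings. If the sponsor prefers listings alone, Appendix 2 should record the reduction and SAP 5.4 should be reworded; that makes the documents consistent but leaves the endpoints unsummarized.

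The cost is SAP wording and two or three extra safety tables from data already collected.
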